### RECIST 1.1

The following section outlines the RECIST 1.1 guidelines as published (31) and as summarized by National Cancer Institute for CTEP-involved clinical trials.

#### I. Disease Parameters for RECIST 1.1

Changes in the largest diameter (unidimensional measurement) of the tumor lesions and the shortest diameter in the case of malignant lymph nodes are used in the RECIST 1.1 criteria.

Measurable disease. Measurable lesions are defined as those that can be accurately measured in at least one dimension (longest diameter to be recorded) as  $\geq 20$  mm by chest x-ray, as  $\geq 10$  mm with CT scan, or  $\geq 10$  mm with calipers by clinical exam. All tumor measurements must be recorded in millimeters (or decimal fractions of centimeters).

Note: Tumor lesions that are situated in a previously irradiated area might or might not be considered measurable. *If the investigator thinks it appropriate to include them, the conditions under which such lesions should be considered must be defined in the protocol.*

**NOTE for irRECIST: During target lesion selection the radiologist will consider information on the anatomical sites of previous intervention (e.g. previous irradiation, RF-ablation, TACE, surgery, etc.). Lesions undergoing prior intervention will not be selected as target lesions unless there has been a demonstration of progress in the lesion.**

CONFIDENTIAL

Malignant lymph nodes. To be considered pathologically enlarged and measurable, a lymph node must be  $\geq 15$  mm in short axis when assessed by CT scan (CT scan slice thickness recommended to be no greater than 5 mm). At baseline and in follow-up, only the short axis will be measured and followed.

Non-measurable disease. All other lesions (or sites of disease), including small lesions (longest diameter  $< 10$  mm or pathological lymph nodes with  $\geq 10$  to  $< 15$  mm short axis), are considered non-measurable disease. Bone lesions, leptomeningeal disease, ascites, pleural/pericardial effusions, lymphangitis cutis/pulmonitis, inflammatory breast disease, and abdominal masses (not followed by CT or MRI), are considered as non-measurable.

Note: Cystic lesions that meet the criteria for radiographically defined simple cysts should not be considered as malignant lesions (neither measurable nor non-measurable) since they are, by definition, simple cysts. 'Cystic lesions' thought to represent cystic metastases can be considered as measurable lesions, if they meet the definition of measurability described above. However, if non-cystic lesions are present in the same subject, these are preferred for selection as target lesions.

**NOTE for irRECIST:**

**Lesions that are partially cystic or necrotic can be selected as target lesions. The longest diameter of such a lesion will be added to the Total Measured Tumor Burden (TMTB) of all target lesions at baseline. If other lesions with a non-liquid/non-necrotic component are present, those should be preferred.**

**Brain lesions detected on brain scans can be considered as both target or non-target lesions depending on the protocol definition.**

Target lesions. All measurable lesions up to a maximum of 2 lesions per organ and 5 lesions in total, representative of all involved organs, should be identified as target lesions and recorded and measured at baseline. Target lesions should be selected on the basis of their size (lesions with the longest diameter), be representative of all involved organs, but in addition should be those that lend themselves to reproducible repeated measurements. It may be the case that, on occasion, the largest lesion does not lend itself to reproducible measurement in which circumstance the next largest lesion which can be measured reproducibly should be selected. A sum of the diameters (longest for non-nodal lesions, short axis for nodal lesions) for all target lesions will be calculated and reported as the baseline sum diameters. If lymph nodes are to be included in the sum, then only the short axis is added into the sum. The baseline sum diameters will be used as reference to further characterize any objective tumor regression in the measurable dimension of the disease.

Non-target lesions. All other lesions (or sites of disease) including any non-measurable as well as measurable lesions over and above the 5 target lesions should be identified as non-target lesions and should also be recorded at baseline. Measurements of these lesions are not required, but the presence, absence, or in rare cases unequivocal progression of each should be noted throughout follow-up.

---

CONFIDENTIAL

## II. Methods for Evaluation of Measurable Disease

All measurements should be taken and recorded in metric notation using a ruler or calipers. All baseline evaluations should be performed as closely as possible to the beginning of treatment and never more than 4 weeks before the beginning of the treatment.

The same method of assessment and the same technique should be used to characterize each identified and reported lesion at baseline and during follow-up. Imaging-based evaluation is preferred to evaluation by clinical examination unless the lesion(s) being followed cannot be imaged but are assessable by clinical exam.

Clinical lesions: Clinical lesions will only be considered measurable when they are superficial (e.g., skin nodules and palpable lymph nodes) and  $\geq 10$  mm diameter as assessed using calipers (e.g., skin nodules). In the case of skin lesions, documentation by color photography, including a ruler to estimate the size of the lesion, is recommended.

Chest x-ray: Lesions on chest x-ray are acceptable as measurable lesions when they are clearly defined and surrounded by aerated lung. However, CT is preferable.

Conventional CT and MRI: This guideline has defined measurability of lesions on CT scan based on the assumption that CT slice thickness is 5 mm or less. If CT scans have slice thickness greater than 5 mm, the minimum size for a measurable lesion should be twice the slice thickness. MRI is also acceptable in certain situations (e.g. for body scans).

Use of MRI remains a complex issue. MRI has excellent contrast, spatial, and temporal resolution; however, there are many image acquisition variables involved in MRI, which greatly impact image quality, lesion conspicuity, and measurement. Furthermore, the availability of MRI is variable globally. As with CT, if an MRI is performed, the technical specifications of the scanning sequences used should be optimized for the evaluation of the type and site of disease. Furthermore, as with CT, the modality used at follow-up should be the same as was used at baseline and the lesions should be measured/assessed on the same pulse sequence. It is beyond the scope of the RECIST guidelines to prescribe specific MRI pulse sequence parameters for all scanners, body parts, and diseases. Ideally, the same type of scanner should be used and the image acquisition protocol should be followed as closely as possible to prior scans. Body scans should be performed with breath-hold scanning techniques, if possible.

PET-CT: At present, the low dose or attenuation correction CT portion of a combined PET-CT is not always of optimal diagnostic CT quality for use with RECIST measurements. However, if the site can document that the CT performed as part of a PET-CT is of identical diagnostic quality to a diagnostic CT (with IV and oral contrast), then the CT portion of the PET-CT can be used for RECIST measurements and can be used interchangeably with conventional CT in accurately measuring cancer lesions over time. Note, however, that the PET portion of the CT introduces additional data which may bias an investigator if it is not routinely or serially performed.

Ultrasound: Ultrasound is not useful in assessment of lesion size and should not be used as a method of measurement. Ultrasound examinations cannot be reproduced in their entirety for independent review at a later date and, because they are operator dependent, it cannot be guaranteed that the same technique and measurements will be taken from one assessment to

---

CONFIDENTIAL

the next. If new lesions are identified by ultrasound in the course of the study, confirmation by CT or MRI is advised. If there is concern about radiation exposure at CT, MRI may be used instead of CT in selected instances.

Endoscopy, Laparoscopy: The utilization of these techniques for objective tumor evaluation is not advised. However, such techniques may be useful to confirm complete pathological response when biopsies are obtained or to determine relapse in trials where recurrence following complete response (CR) or surgical resection is an endpoint.

Tumor markers: Tumor markers alone cannot be used to assess response. If markers are initially above the upper normal limit, they must normalize for a subject to be considered in complete clinical response. Specific guidelines for both CA-125 response (in recurrent ovarian cancer) and PSA response (in recurrent prostate cancer) have been published.(35-37) In addition, the Gynecologic Cancer Intergroup has developed CA-125 progression criteria which are to be integrated with objective tumor assessment for use in first-line trials in ovarian cancer.(38)

Cytology, Histology: These techniques can be used to differentiate between partial responses (PR) and complete responses (CR) in rare cases (e.g., residual lesions in tumor types, such as germ cell tumors, where known residual benign tumors can remain).

The cytological confirmation of the neoplastic origin of any effusion that appears or worsens during treatment when the measurable tumor has met criteria for response or stable disease is mandatory to differentiate between response or stable disease (an effusion may be a side effect of the treatment) and progressive disease.

FDG-PET: While FDG-PET response assessments need additional study, it is sometimes reasonable to incorporate the use of FDG-PET scanning to complement CT scanning in assessment of progression (particularly possible 'new' disease). New lesions on the basis of FDG-PET imaging can be identified according to the following algorithm:

- a) Negative FDG-PET at baseline, with a positive FDG-PET at follow-up is a sign of PD based on a new lesion.
- b) No FDG-PET at baseline and a positive FDG-PET at follow-up: If the positive FDG-PET at follow-up corresponds to a new site of disease confirmed by CT, this is PD. If the positive FDG-PET at follow-up is not confirmed as a new site of disease on CT, additional follow-up CT scans are needed to determine if there is truly progression occurring at that site (if so, the date of PD will be the date of the initial abnormal FDG-PET scan). If the positive FDG-PET at follow-up corresponds to a pre-existing site of disease on CT that is not progressing on the basis of the anatomic images, this is not PD.
- c) FDG-PET may be used to upgrade a response to a CR in a manner similar to a biopsy in cases where a residual radiographic abnormality is thought to represent fibrosis or scarring. The use of FDG-PET in this circumstance should be prospectively described in the protocol and supported by disease-specific medical literature for the indication. However, it must be acknowledged that both approaches may lead to false positive CR due to limitations of FDG-PET and biopsy resolution/sensitivity.

---

CONFIDENTIAL

Note: A 'positive' FDG-PET scan lesion means one which is FDG avid with an uptake greater than twice that of the surrounding tissue on the attenuation corrected image.

### III. Response Criteria for RECIST 1.1

#### A. Evaluation of Target Lesions

Complete Response (CR): Disappearance of all target lesions. Any pathological lymph nodes (whether target or non-target) must have reduction in short axis to <10 mm.

Partial Response (PR): At least a 30% decrease in the sum of the diameters of target lesions, taking as reference the baseline sum diameters

Progressive Disease (PD): At least a 20% increase in the sum of the diameters of target lesions, taking as reference the smallest sum on study (this includes the baseline sum if that is the smallest on study). In addition to the relative increase of 20%, the sum must also demonstrate an absolute increase of at least 5 mm. (Note: the appearance of one or more new lesions is also considered progressions).

Stable Disease (SD): Neither sufficient shrinkage to qualify for PR nor sufficient increase to qualify for PD, taking as reference the smallest sum diameters while on study

#### B. Evaluation of Non-Target Lesions

Complete Response (CR): Disappearance of all non-target lesions and normalization of tumor marker level. All lymph nodes must be non-pathological in size (<10 mm short axis)

Note: If tumor markers are initially above the upper normal limit, they must normalize for a subject to be considered in complete clinical response.

Non-CR/Non-PD: Persistence of one or more non-target lesion(s) and/or maintenance of tumor marker level above the normal limits

Progressive Disease (PD): Appearance of one or more new lesions and/or *unequivocal progression* of existing non-target lesions. *Unequivocal progression* should not normally trump target lesion status. It must be representative of overall disease status change, not a single lesion increase.

Although a clear progression of "non-target" lesions only is exceptional, the opinion of the treating physician should prevail in such circumstances, and the progression status should be confirmed at a later time by the review panel (or Principal Investigator).

#### C. Evaluation of Best Overall Response

The best overall response is the best response recorded from the start of the treatment until disease progression/recurrence (taking as reference for progressive disease the smallest measurements recorded since the treatment started). The subject's best response assignment will depend on the achievement of both measurement and confirmation criteria.

---

CONFIDENTIAL

**1. For Subjects with Measurable Disease (i.e., Target Disease)**

Target Lesions	Non-Target Lesions	New Lesions	Overall Response	Best Overall Response when Confirmation is Required*
CR	CR	No	CR	≥4 wks. Confirmation**
CR	Non-CR/Non-PD	No	PR	≥4 wks. Confirmation**
CR	Not evaluated	No	PR	
PR	Non-CR/Non-PD/not evaluated	No	PR	documented at least once ≥4 wks. from baseline**
SD	Non-CR/Non-PD/not evaluated	No	SD	
PD	Any	Yes or No	PD	no prior SD, PR or CR
Any	PD***	Yes or No	PD	
Any	Any	Yes	PD	

\* See RECIST 1.1 manuscript for further details on what is evidence of a new lesion.  
 \*\* Only for non-randomized trials with response as primary endpoint.  
 \*\*\* In exceptional circumstances, unequivocal progression in non-target lesions may be accepted as disease progression.  
 Note: Subjects with a global deterioration of health status requiring discontinuation of treatment without objective evidence of disease progression at that time should be reported as “*symptomatic deterioration.*” Every effort should be made to document the objective progression even after discontinuation of treatment.

**2. For Subjects with Non-Measurable Disease (i.e., Non-Target Disease)**

Non-Target Lesions	New Lesions	Overall Response
CR	No	CR
Non-CR/non-PD	No	Non-CR/non-PD*
Not all evaluated	No	not evaluated
Unequivocal PD	Yes or No	PD
Any	Yes	PD

\* ‘Non-CR/non-PD’ is preferred over ‘stable disease’ for non-target disease since SD is increasingly used as an endpoint for assessment of efficacy in some trials so to assign this category when no lesions can be measured is not advised.

**D. Duration of Response**

Duration of overall response: The duration of overall response is measured from the time measurement criteria are met for CR or PR (whichever is first recorded) until the first date that recurrent or progressive disease is objectively documented (taking as reference for progressive disease the smallest measurements recorded since the treatment started).

The duration of overall CR is measured from the time measurement criteria are first met for CR until the first date that progressive disease is objectively documented.

Duration of stable disease: Stable disease is measured from the start of the treatment until the criteria for progression are met, taking as reference the smallest measurements recorded since the treatment started, including the baseline measurements.

CONFIDENTIAL

## irRECIST

Immune-related RECIST (irRECIST) guidelines according to Bohnsack et al. (34) are presented below.

### I. Baseline Assessments in irRECIST

In irRECIST, baseline assessment and measurement of measurable/non-measurable and target/non-target lesions and lymph nodes are in line with RECIST 1.1. One new definition is added: If a subject has no measurable and no non-measurable disease at baseline the radiologist will assign 'No Disease' (irND) as the overall tumor assessment for any available follow-up time points unless new measurable lesions are identified and contribute to the total measured tumor burden (TMTB). irND is a valid assessment in studies with adjuvant setting where the protocol and study design allow the inclusion of subjects with no visible disease.

### II Follow-up Assessments in irRECIST

#### *A. Follow-up recording of target and new measurable lesions*

**A key difference in irRECIST is that the appearance new lesions does not automatically indicate progression. Instead, all measured lesions (baseline-selected target lesions and new measurable lesions) are combined into the total measured tumor burden (TMTB) at follow up. Baseline-selected target lesions and new measurable lesions are NOT assessed separately. Measurements of those lesions are combined into the TMTB, and one combined assessment provided.**

In order to be selected as new measurable lesions ( $\leq 2$  lesions per organ,  $\leq 5$  lesions total, per time point), new lesions must meet criteria as defined for baseline target lesion selection and meet the same minimum size requirements of 10 mm in long diameter and minimum 15 mm in short axis for new measurable lymph nodes. New measurable lesions should be prioritized according to size, and the largest lesions elected as new measured lesions.

#### *B. Follow-up non-target assessment*

RECIST 1.1 definitions for assessment of non-target lesions apply. The response of non-target lesions primarily contributes to the overall response assessments of irCR and irNon-CR/Non-PD (irNN). Non-target lesions do not affect irPR and irSD assessments. Only a massive and unequivocal worsening of non-target lesions alone, even without progress in the TMTB is indicative of irPD. In alignment with RECIST 1.1, baseline selected non-target lesions can never convert to measurable lesions, not even if they increase in size at subsequent time points and become measurable. Only true new lesions can be measured and contribute to the TMTB.

#### *C. Follow-up for New Non-Measurable Lesions*

All new lesions not selected as new measurable lesions are considered new non-measurable lesions and are followed qualitatively. Only a massive and unequivocal progression of new non-measurable lesions leads to an overall assessment of irPD for the time point. Persisting new non-measurable lesions prevent irCR.

---

CONFIDENTIAL

### III Overall Assessments for irRECIST

The irRECIST overall tumor assessment is based on TMTB of measured target and new lesions, non-target lesion assessment and new non-measurable lesions.

At baseline, the sum of the longest diameters (SumD) of all target lesions (up to 2 lesions per organ, up to total 5 lesions) is measured. At each subsequent tumor assessment, the SumD of the target lesions and of new, measurable lesions (up to 2 new lesions per organ, total 5 new lesions) are added together to provide the total measurable tumor burden (TMTB).

Overall Assessments by irRECIST	
Complete Response (irCR)	Complete disappearance of all measurable and non-measurable lesions. Lymph nodes must decrease to < 10 mm in short axis.
Partial Response (irPR)	
Decrease of <math>\geq 30\%</math> in TMTB relative to baseline, non-target lesions are irNN, and no unequivocal progression of new non-measurable lesions
 
 
If new measurable lesions appear in subjects with no target lesions at baseline, irPD will be assessed. That irPD time point will be considered a new baseline, and all subsequent time points will be compared to it for response assessment. irPR is possible if the TMTB of new measurable lesions decreases by <math>\geq 30\%</math> compared to the first irPD documentation
 
irRECIST can be used in the adjuvant setting, in subjects with no visible disease on CT/MRI scans. The appearance of new measurable lesion(s) automatically leads to an increase in TMTB by 100% and leads to irPD. These subjects can achieve a response if the TMTB decreases at follow-up, as a sign of delayed response.
 
Based on the above, sponsors may consider enrolling subjects with no measurable disease and/or no visible disease in studies with response related endpoints.
 

Stable Disease (irSD)	Failure to meet criteria for irCR or irPR in the absence of irPD
Progressive Disease (irPD)	
Minimum 20% increase and minimum 5 mm absolute increase in TMTB compared to nadir, or irPD for non-target or new non-measurable lesions. Confirmation of progression is recommended minimum 4 weeks after the first irPD assessment. An irPD confirmation scan may be recommended for subjects with a minimal TMTB %-increase over 20% and especially during the flare time-window of the first 12 weeks of treatment, depending on the compound efficacy expectations, to account for expected delayed response.
 
 
In irRECIST a substantial and unequivocal increase of non-target lesions is indicative of progression.
 
IrPD may be assigned for a subject with multiple new non-measurable lesions if they are considered to be a sign of unequivocal massive worsening
 

Other	
irNE: used in exceptional cases where insufficient data exist.
 
irND: in adjuvant setting when no disease is detected
 
irNN: no target disease was identified at baseline, and at follow-up the subject fails to meet criteria for irCR or irPD

CONFIDENTIAL

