### 5.1 Inclusion Criteria

Eligible subjects ***must fulfill*** all of the following criteria:

1.	
Histologic confirmation of metastatic NSCLC.            For subjects with known EGFR or ALK/ROS-1 mutations, prior therapy must have included an EGFR tyrosine kinase inhibitor or ALK/ROS-1 inhibitor, respectively.            Subjects may have had 1 prior line of anti-PD-1/PD-L1 therapy. Subjects who received prior anti-PD-1/PD-L1 therapy must have progressed during or after treatment, but not prior to Week 12 of treatment.
																
2.	
Measurable disease according to RECIST 1.1, defined as <math>\geq 1</math> lesion that can be accurately measured in at least 1 dimension (longest diameter to be recorded for non-lymph node lesions, shortest diameter to be recorded for lymph node lesions). Each lesion must be <math>\geq 10</math> mm when measured by CT, MRI, or caliper measurement by clinical examination or <math>\geq 20</math> mm when measured by chest x-ray.             NOTE: Per Amendment 9.1, biopsies should not be taken from a target lesion unless that is the only suitable lesion, in which case it should be of reasonable size (refer to Section 4.3.1.1).
																
3.	
Willing to undergo a pre-treatment biopsy, or if not feasible, availability of archival (diagnostic) specimens.
																
4.	
Subjects with treated brain metastases must have been treated with surgery and/or radiation therapy <math>\geq 21</math> days pre-study and must be clinically stable with no requirement for steroids.
																

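### The irRECIST partial-response row contradicts the section's own rule on non-target lesions and relies on a term with two meanings, so irRECIST ORR, best overall response and DoR depend on which text is followed; the lesion sum also conflicts with the nodal short-axis rule

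*Protocol*

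**What the plan says.** Protocol Section 4.2.1 and SAP Section 2.2 assess efficacy by both irRECIST and RECIST 1.1. The rules stand in Protocol Section 8.5.

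On non-target lesions, the irRECIST part says:

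- Overall-assessment table, irPR row: a TMTB decrease of at least 30% from baseline, with the added condition "non-target lesions are irNN, and no unequivocal progression of new non-measurable lesions".
- Section II.B, follow-up of non-target lesions: "Non-target lesions do not affect irPR and irSD assessments". The same paragraph introduces irNN as the non-target result: "The response of non-target lesions primarily contributes to the overall response assessments of irCR and irNon-CR/Non-PD (irNN").
- Last row of the table: irNN means "no target disease was identified at baseline, and at follow-up the subject fails to meet criteria for irCR or irPD".
- irSD row: "Failure to meet criteria for irCR or irPR in the absence of irPD".

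Inclusion criterion 2 in Protocol Section 5.1 requires "Measurable disease according to RECIST 1.1, defined as" at least one accurately measurable lesion.

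On diameters, the paragraph above the table builds the sum as follows: "At baseline, the sum of the longest diameters (SumD) of all target lesions", with no exception for lymph nodes. The RECIST 1.1 part says of malignant nodes: "At baseline and in follow-up, only the short axis will be measured and followed". Its target-lesion paragraph sums the longest diameter for non-nodal lesions and the short axis for nodes. Section I of the irRECIST part aligns baseline measurement, nodes included, with RECIST 1.1. Section II.A sizes new measurable nodes by short axis, and inclusion criterion 2 records the shortest diameter for nodes.

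**The concern.** The irPR row and Section II.B cannot both be applied. One makes non-target status a condition for a partial response; the other says it plays no part. Because irSD is the residual category, a subject who fails only the irNN condition becomes irSD. Under one reading of irNN the rule also runs backwards: complete disappearance of the non-target disease gives a worse overall category than its persistence.

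Two analysts who each follow the protocol could therefore report different irRECIST ORR, best overall response and DoR from the same scans. SAP Section 7 does not settle it. It gives no rule for combining target and non-target status, and none for nodal diameters.

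The diameter wording is a second, separate conflict. TMTB feeds both the 30% threshold for irPR and the 20% and 5 mm thresholds for irPD. For subjects with nodal target lesions or new measurable nodes, the two ways of summing can fall on different sides of these thresholds.

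**Working it through.** The plan gives no figure on this point, so the check compares texts, with arithmetic only for size.

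**1. Category under each reading.** Take a subject with target lesions, TMTB down 40%, no new non-measurable lesions and no irPD.

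| Non-target state | Section II.B rule | irPR row, irNN = Non-CR/Non-PD | irPR row, irNN = no target disease at baseline |
|---|---|---|---|
| Non-CR/Non-PD | irPR | irPR | irSD |
| CR | irPR | irSD | irSD |
| Not evaluated | irPR | irSD | irSD |
| None at baseline | irPR | irSD (contestable) | irSD |

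The second row is not irCR, because target lesions remain. The last column is irSD throughout because inclusion criterion 2 requires measurable disease, so subjects enrolled as intended have target disease.

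**2. Size for ORR.** Protocol Section 3.1.6 plans 20 subjects per arm, so one reclassified subject moves ORR by 1/20 = 5 points. As an illustration only, assume 5 of 20 subjects meet irPR under Section II.B. With exact binomial (Clopper-Pearson) intervals:

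| Moved to irSD | ORR | 95% CI |
|---|---|---|
| 0 | 5/20 = 25% | 8.7 to 49.1% |
| 1 | 4/20 = 20% | 5.7 to 43.7% |
| 2 | 3/20 = 15% | 3.2 to 37.9% |
| 3 | 2/20 = 10% | 1.2 to 31.7% |
| 4 | 1/20 = 5% | 0.1 to 24.9% |
| 5 | 0/20 = 0% | 0 to 16.8% |

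The intervals for 1 to 5 of 20 agree with the table in Protocol Section 3.1.6. DCR counts SD, PR and CR (Protocol Section 4.2.1.2), so a move from irPR to irSD leaves it unchanged.

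**3. Diameter wording.** The lesions are assumed, in mm; each is one non-nodal lesion plus one node (long x short axis).

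| Baseline | Follow-up | Longest diameters | Short axis for node |
|---|---|---|---|
| 20; 30x18 | 15; 27x10.5 | 50 to 42, -16.0% | 38 to 25.5, -32.9% |
| 20; 30x18 | 15; 18x15 | 50 to 33, -34.0% | 38 to 30, -21.1% |
| 20; 30x20 | 14; 21x14 | 50 to 35, -30.0% | 40 to 28, -30.0% |
| 20; 30x16 | 20; 30x24 | 50 to 50, 0% | 36 to 44, +22.2% (+8 mm) |

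Relative to the short-axis rule, longest diameters lose a response in the first case, gain one in the second, change nothing in the third, and miss an irPD in the fourth.

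**The case against.** The best defence is that a sensible reader would not be misled. Section II.B is explicit, and reading irNN as a subject-level category inside a phrase about lesions is the least natural choice. A condition on non-target lesions can also be taken as met when there are none. On diameters, four other places give the short axis for nodes, so the longest-diameter phrase looks like loose shorthand. If sites follow those places, nodal long axes may not be recorded at all. Much of this stands. It makes the harm conditional, but it does not reconcile the texts, and the table is where a programmer would look first.

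Several stronger inferences are tempting and are not supported:

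- That true responders will be classified as stable disease. This happens only if the irPR row is applied over Section II.B; the documents do not say which prevails.
- That the irRECIST table alone governs response. RECIST 1.1 results are reported too.
- That non-target CR separates irRECIST from RECIST 1.1. The protocol's RECIST 1.1 table also has no row for target PR with non-target CR, although it does accept non-target lesions that were not evaluated.
- That the irNN condition affects DCR or treatment beyond progression. DCR counts irSD, and the irPD row has no irNN condition.
- That longest diameters bias ORR downwards. The direction is not fixed.

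**Conclusion.** The point holds as an internal contradiction in a written classification rule, and it is minor. The irPR row and Section II.B disagree, irNN is defined twice, and the SAP resolves neither. The exposed results are irRECIST ORR, best overall response and DoR, which are secondary and descriptive. The irNN conflict leaves DCR and the primary safety endpoints unaffected.

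The size is 5 ORR points per affected subject in a 20-subject arm. How many subjects would be affected is unknown: the documents do not say how often non-target lesions would be in CR, not evaluated or absent in a subject whose TMTB falls enough. The 5-of-20 starting point is an assumption.

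The diameter conflict is real but narrower. It concerns only subjects with nodal target lesions or new measurable nodes. Because irPD uses the same sum, it can also move irRECIST progression, and with it PFS and DCR, in either direction.

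**What to change.** Before irRECIST response is derived, make two wording changes in Protocol Section 8.5 and repeat both rules in SAP Section 7:

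1. Align the irPR row with Section II.B: TMTB is down by at least 30% from baseline, the non-target lesions do not meet irPD, and new non-measurable lesions have not unequivocally progressed. This removes irNN from the row and leaves its subject-level meaning intact.
2. Define SumD and TMTB, for target and new measurable lesions, with the longest diameter for non-nodal lesions and the short axis for nodes, in line with the RECIST 1.1 part and Section I of the irRECIST part.

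The cost is two phrases in the protocol and two derivation rules in the SAP. The nodal short axis is already to be recorded, so no new scans or measurements are needed.
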